The study team originally planned to collect exacerbation data to compare 12 months pre-initial visit to 12 months post-initial visit among patients from third-party payer sites. However, these sites were unable to participate in the study. Therefore, high performing sites were selected to recontact their participants to ask if they would be willing to participate in a chart review to be conducted 12 months after their initial study visit. If patients agree, sites will use a new verbal consent script specific for the 12-month post-initial visit exacerbation data. For patients who consent, the site will complete a 12-month post-initial visit exacerbation CRF form. Data will only be collected for patients who provide their verbal consent. Verbal consent will be documented on the 12-month post-initial visit exacerbation CRF form. This will be compared to the exacerbation data 12 months pre-initial visit, which was collected as part of the planned clinician-completed CRF form. Evidera will host a 30-minute conference call with each clinical site for up to four (4) time points (touchpoints) at Months 1, 2, 3 (optional), and 6 to discuss the use of the PRECISION tools, address site questions, and discuss a set of touchpoint questions that focus on the challenges and facilitators of implementing the PRECISION program. These meetings will also be used to identify any sites that may benefit from participating in a re-training session (budget assumes up to six sites will need re-training). The optional month three (3) touchpoint will be based on whether the site is having any difficulties with the study.

After patient enrollment has been completed, prescribing providers at clinical sites, nurse case managers, or the asthma coaches from the telehealth component of Asthma and Allergy Network who treated at least 10 patients will complete the Post-study Survey. Evidera will provide the participating HCP with Post-study Survey, via an email PDF attachment (to be self-completed by the HCP). The emailed survey will have a pre-populated header with a unique participant ID number.

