 No other health conditions	 Chronic Obstructive Pulmonary Disease (COPD)
 Allergy diagnosed by blood or skin testing	 Chronic sinusitis
 Allergic rhinitis (nasal allergies, "hay fever")	 Depression
 Aeroallergens	 Diabetes
 Heart disease (history of heart attack, heart failure, or heart valve problems)	 Emphysema
 Anxiety	 GERD (heartburn/reflux)
 Anaphylaxis (severe allergic reaction to a food, bee sting, allergy shot, medication, or other)	 Hypertension (high blood pressure)
 Arthritis	 Nasal Polyps
 Aspirin sensitivity (aspirin causes hives, swelling, or breathing problems)	 Sleep Apnea
 Atopic dermatitis/Eczema	 Stroke
 Chronic bronchitis	 Other (specify): _____
	 Unknown

14. Was spirometry lung function testing performed on this patient in the last 12 months?

[figure not shown]
[figure not shown]
Yes (Record below): Date of most recent spirometry   

[figure not shown]
[figure not shown]
No

[figure not shown]
[figure not shown]
Pre-bronchodilator

[figure not shown]
FVC:  L
 % (predicted)

[figure not shown]
Post-bronchodilator

FVC:  L
 % (predicted)

FEV1:  L
 % (predicted)

FEV1:  L
 % (predicted)

FEV1/FVC ratio 

FEV1/FVC ratio 

Not Available

Not Available

Evidera 138	Site	Page 6 of 7
		
Evidera # 138	Plate # 006	Visit # 001
Participant ID		

15. Please indicate asthma exacerbation history within the prior 12 months:

ASTHMA EXACERBATION HISTORY		 Not applicable				
An asthma exacerbation is defined by a change in asthma control requiring a course of oral steroids (i.e., at least 3 days with at least 10 days between each burst) and/or steroid injection and/or a hospitalization for asthma or emergency department visit for an asthma exacerbation. Importantly, record only the highest utilization for each exacerbation, do not double count exacerbation episodes. If an OCS course was due to a hospitalization, do not record as OCS course but as the hospitalization						

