15.5 Date of most current exacerbation:   unknown						
MMM	YYYY					

Evidera 138 Site Page 7 of 7

Evidera # 138 Plate # 007 Visit # 001

Participant ID

██████████

16. Following the use of the PRECISION program, which of the following will you do to the patient's medication after today's telehealth visit? (check all that apply)

- Step-down of controller medicines
- No change to the level of controller therapy
- Step-up of controller medicines
- Prescribe a course of systemic corticosteroids
- Begin work-up for possible biologic
- Begin biologic: (specify): _____
- Other: (specify): _____

Part 4. Asthma Checklist (Assess content only)

1. Please check the Asthma Checklist Assess items (page 1) that were considered during the visit:

CONSIDER FOR ALL PATIENTS REGARDLESS OF ASTHMA CONTROL		CONSIDER FOR PATIENTS WITH UNCONTROLLED SYMPTOMS AND/OR RISK FACTORS FOR EXACERBATIONS	
 Adherence ^{1,3}	 Appropriate Therapy ^{1,3}	 Asthma Phenotyping ^{1,4}	 Referral to an Asthma Specialty Center, or Other Appropriate Specialist or Health Care Provider in Your Area ^{1,2}
 Asthma Action Plan ^{1,2,4}	 Comorbidities ^{1,2}	 Home and/or Work Exposures ^{1,2,4}	 Alternative Diagnoses and Hidden Comorbidities ^{1,2}
 Inhaler Technique ^{1,2,4}			 Optimizing Therapy with Add-on or Advanced Treatment ^{1,3}
 Psychological Issues ^{1,2}			
 Spirometry ^{1,2,4}			
 Tobacco Use ^{1,2,5}			
 Vaccinations ^{1,2,6,7}			

Investigator/Coordinator Signature: _____

Date:

DD	MMM	2	0	

 YYYY

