3. ANALYSIS SET

- **All enrolled patients:** All enrolled patients who have completed the initial visit with the AIRQ®
- **Web-survey analysis dataset:** All enrolled patients who complete the initial visit and the web survey
- **Primary care cluster dataset:** All enrolled patients at a primary care site who complete the initial visit and the web survey **CCI**.
- **Exacerbation dataset:** Includes EMR or claims data for enrolled patients who completed the initial visit and have available pre-post exacerbation data.
- **Follow-up analysis set:** All enrolled patients who completed the initial visit with the AIRQ® and have at least one follow-up visit completed in the nine-month implementation period with the follow-up AIRQ®. Patients are not required to have a follow-up visit.
- **HCP analysis set:** All health care providers trained on the study who complete the post-study survey and/or qualitative interview

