6. BIAS

6.1 Methods to Minimize Bias

Given that completing the ACE Questionnaire is optional, the potential for response bias (e.g., patients who like the telehealth platform may be more inclined to complete the survey) may be introduced into this study. This will be noted when interpreting the results. Additionally, patients who have a follow-up assessment may be more severe than those who do not; thus, change scores may not be representative of the entire sample, which will also be noted when interpreting results.

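### The pre/post exacerbation comparison is uncontrolled, rests on re-consenting patients at undefined 'high performing' sites, and has no visible rule for an attack that prompted the initial visit, so a fall could occur without any program effect

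*Protocol*

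**What the plan says.** **Sample.** Protocol 3.1 and 6.1.2 explain that the third-party payer sites planned for this comparison could not take part. Instead, "high performing sites were selected to recontact their participants to ask if they would be willing to participate in a chart review". A new verbal consent is needed: "Data will only be collected for patients who provide their verbal consent". The visible text does not define 'high performing' and gives neither the number of sites nor an expected consent rate.

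**Comparison.** For the post-visit data, 6.1.2 states: "This will be compared to the exacerbation data 12 months pre-initial visit, which was collected as part of the planned clinician-completed CRF form". No concurrent comparator is visible.

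**Windows.** The initial CRF (Appendix I, item 15) asks: "Please indicate asthma exacerbation history within the prior 12 months". Item 15.3 takes dates of unplanned clinic visits. Item 15.5, "Date of most current exacerbation", takes a month and year or 'unknown'. Items 15.1, 15.2 and 15.4 are undated. The 12-month post-visit form (Appendix J) refers in its header to the period since the initial visit, but its items count events since the last visit.

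**Entry.** Protocol 3.2 and 6.1.2 enrol patients presenting for any telehealth or in-person visit, found mainly through schedules and record review. The follow-up CRF asks the reason for the visit and offers exacerbation as an answer. The initial CRF has no such item.

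**SAP.** Section 3 defines the exacerbation dataset thus: "Includes EMR or claims data for enrolled patients who completed the initial visit and have available pre-post exacerbation data". Section 6.1 covers questionnaire response ("Given that completing the ACE Questionnaire is optional, the potential for response bias" and so on) and the severity of patients who return for follow-up. Neither it nor Protocol 5.2 mentions the pre/post comparison. SAP Appendix B shows that within-patient change in OCS use was tested (Bowker's test, Table 31b).

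**The concern.** A patient who enters the study because of a recent attack carries that attack into the year before the visit. The year after the visit has no such anchor. The pre-visit count is then raised by the way patients enter, and a return to the usual rate looks like improvement. With no control group, the comparison cannot separate this from an effect of the program.

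The sample adds a second problem. It consists of patients who agreed to be recontacted, at sites chosen on an unstated criterion, and the SAP definition does not tell the reader so. Without a comparison against the other enrolled patients, nobody can judge whom the result describes.

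At stake is how a fall in exacerbations is read. A reader could take it as a benefit of the program, and the visible plan contains no caution against that.

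**Working it through.** The documents give no sample size, rate, effect or power for this comparison, so there is no plan figure to reproduce. Every rate, share, sample size and consent probability below is an assumption.

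**1. Attack that prompts the visit, simple form.** Let the background rate be 1 per year in both years, with no program effect, and let a share q of initial visits follow one extra attack counted in the pre-visit year. Then pre = 1 + q and post = 1, so the apparent fall is q/(1 + q).

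- q = 0: 0%
- q = 0.10: 0.10/1.10 = 9.1%
- q = 0.40: 0.40/1.40 = 28.6%

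**2. Patients who differ in risk.** Let personal rates follow a gamma distribution with mean μ and squared coefficient of variation k, with yearly counts Poisson. Attack-driven visits then over-represent high-risk patients: post = μ(1 + qk), pre = post + q, fall = q/[μ(1 + qk) + q]. Example: μ = 1, k = 1, q = 0.2 gives post 1.2, pre 1.4 and a fall of 0.2/1.4 = 14.3%.

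| q | fall, μ 0.5 to 1.5 and k 0.5 to 1.0 |
|---|---|
| 0 | 0% |
| 5% | 3.1 to 8.9% |
| 10% | 5.7 to 16.0% |
| 20% | 10.0 to 26.7% |
| 30% | 13.3 to 34.3% |

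In simulation with 200 patients, μ = 1 and k = 1, a paired test (upper tail of a two-sided 5% test) called this null fall significant in 2.4% of runs at q = 0, 16% at 10%, 43% at 20% and 70% at 30%.

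**3. Re-consent alone** (q = 0, μ = 1, k = 1, simulated).

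| consent depends on | apparent change |
|---|---|
| underlying risk only | about 0 |
| pre-year event: 0.7 with, 0.5 without | 7.1% fall |
| post-year event: 0.5 with, 0.7 without | 9.0% fall |
| post-year event: 0.7 with, 0.5 without | 7.7% rise |

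Selection therefore has no fixed direction.

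**4. What a sensitivity analysis must do.** Excluding the visit month and the month before covers 1 to 2 months, depending on the day of the visit.

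*Dropping events only.* At 1 per year, the chance of a background event in that period is 1 − exp(−1/12) = 8.0% to 1 − exp(−2/12) = 15.4%. If no visit is attack-driven and one such event is removed per patient, the pre rate becomes 0.920 to 0.846. The result is a false rise of 1/0.920 − 1 = 8.7% to 1/0.846 − 1 = 18.1%.

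*Dropping events and person-time.* Write w for the excluded fraction of the year and p for the chance above. Suppose only one event per patient can be dated and removed, and any prompting attack lies in the excluded period. The pre rate is then [(1 − w) + (1 − q)(w − p) + qw]/(1 − w).

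- q = 0.10, one month: (0.9167 + 0.0030 + 0.0083)/0.9167 = 1.012, a fall of 1.2%
- q = 0.40, two months: (0.8333 + 0.0079 + 0.0667)/0.8333 = 1.090, a fall of 8.2%

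The 9 to 29% null fall thus shrinks to about 1 to 8%. If every event in the period could be dated and removed, it would be 0.

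**5. Post-visit form.** If its items are read literally as since the last visit, and a share f of patients had a follow-up visit at m months, the count loses f × m/12. This is 0.25 × 3/12 = 6% to 0.50 × 6/12 = 25%, again an apparent fall.

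**The case against.** Three objections have force.

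- **Entry is not anchored on an attack.** Any clinic visit qualifies, scheduled ones included, and the share of attack-driven visits is not given. A reader might infer that a fall is likely without any program effect. The documents do not support that: at a share of 0 there is no artefact, and at 5% it is 3 to 9%. Only 'could occur' is supported. A share of exactly zero has no support either, since the initial CRF lists a course of systemic corticosteroids among the actions after the visit.
- **Selection need not cause a fall.** A reader might infer that choosing sites and re-consenting patients pushes the result downward. Step 3 shows that it can push either way or not at all. Nothing says that 'high performing' refers to asthma outcomes. Nor does the text date the recontact; only the chart review is placed 12 months after the initial visit.
- **The exploratory text is redacted** (Protocol 2.3, 4.2.3 and 5.1.3; SAP 1.3, 4.2.3 and 5.1.3). A handling rule or caveat may stand there, so one cannot say that the plan definitely keeps the prompting attack. It is also unclear which window takes an attack treated at the initial visit itself.

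It is also fair to say that the comparison is not among the visible primary or secondary outcomes, and that no visible text claims an effect on exacerbations. These objections limit the strength of the point. They do not touch the visible analysis-set definition or the visible bias sections, which are incomplete as they stand.

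**Conclusion.** The point holds in limited form. The comparison is within-patient and uncontrolled, it is confined to re-consenting patients at sites chosen on an undefined criterion, and no visible rule covers an attack that prompted the initial visit. A fall could therefore appear with no program effect.

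The size depends on a share that the documents do not report: 0, 9 or 29% for assumed shares of 0, 10 or 40% at 1 exacerbation per year, with other rates and heterogeneity shown above. Site selection and re-consent limit generalisability, and the direction of any bias from them is unknown. The SAP's definition by EMR or claims data does not match the sample in the Protocol. The change should be made because it uses data already held and alters what may be concluded, although the comparison is not among the visible primary or secondary outcomes.

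**What to change.** In the SAP:

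1. **Redefine the exacerbation set** as re-consented patients at the selected sites who have the 12-month post-visit CRF, and state how the sites were selected. Tabulate this set against all other enrolled patients on prior-year exacerbations, AIRQ control level and HCP-rated severity from the initial CRF and AIRQ. Report the numbers contacted, consenting and declining.
2. **Add a sensitivity analysis on the total exacerbation count.** Exclude the visit month and the month before from the pre-visit window, using the item 15.5 month and the item 15.3 dates. Remove events in that period and shorten the pre-visit person-time to match. Compare rates per month and show the result beside the unadjusted one as a bracket on how the prompting attack is handled. State which window takes an attack treated at the initial visit.
3. **Reconcile the post-visit form's** header with its items, and say which period the sites actually recorded.
4. **Extend SAP 6.1** to say that regression to the mean, selection and the lack of a control mean that the change is not to be attributed to the program.

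The cost is one table, one sensitivity run and some wording; the tables and the run need no new patient data. There are limits. Dates are partial or may be unknown. Items 15.1, 15.2 and 15.4 are undated, so the OCS shift table cannot be corrected this way. Some bias remains (about 1 to 8% in the illustration), so the bracket is not a pair of bounds. Appendix B is written in the past tense; if results are already known, the added analysis should be labelled post hoc.

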6.1.3 Quality Control

6.1.3.1 Responsibilities

Evidera Responsibilities	Clinical Site Responsibilities	Website Host Responsibilities
Contract directly with clinical sites	Complete and return all institutional review board (IRB)-required documentation to Evidera, as needed	

Evidera Responsibilities	Clinical Site Responsibilities	Website Host Responsibilities
Develop and provide to sites all necessary IRB materials and forms for the patient screening process	Participate in a 60-minute training session about the study, conducted by Evidera	
Submit IRB paperwork on behalf of the sites to the central IRB, or assist sites with local IRB submissions	Ensure that appropriate training has been provided for all staff involved in the study	
Collect, monitor, and store data using DataFax—a direct fax-to-computer (or PDF-to-computer) data management system	Maintain patient confidentiality; Enter patient's email address into the YouGov ³ system on the day of recruitment	
Develop training materials for the training sessions for relevant site investigators and coordinators before study launch	Recruit and screen patients using the Verbal Informed Consent and Recruitment Scripts provided, and obtain verbal consent/assent	
Continually monitor patient recruitment	Track recruitment efforts in the Recruitment Training Log	
Remunerate sites	Provide Evidera project staff with weekly updates on screening and recruitment progress	
Contact sites for data queries on completed or missing forms	Ensure that all necessary questionnaires and forms are completed	Host the study website which includes the Asthma checklist and educational materials, as well as maintain and track all views to the site (i.e., number of time the HCP clicks/PDF views the Asthma Checklist and educational resources)
Lead study closeout procedures, with the help of clinical site staff (e.g., closing out the study with the IRB)	Complete Clinical CRFs for all enrolled patients after interest has been obtained	
Statistical analyses	Designate one staff member to be Evidera's point of contact during implementation, and provide Evidera with that person's direct telephone number	
Adverse event (AE) reporting of AstraZeneca products	Promptly respond to data queries from Evidera	
	Maintain appropriate and confidential project files	

Evidera Responsibilities	Clinical Site Responsibilities	Website Host Responsibilities
	Adhere to all site-related procedures outlined in the protocol	
	Perform required study closeout procedures	
	AE reporting (as outlined in section 6.3)	

Monitoring

Before the first subject is recruited into the study, Evidera will perform the following activities:

- Establish the investigator's capability to appropriately select the sample
- Discuss with the investigator(s) (and other personnel involved in the study) their responsibilities with regards to protocol compliance, and the responsibilities of AstraZeneca or its representatives; this will be documented in a Study Primary Agreement or equivalent between AstraZeneca/delegate and the investigator.

Evidera can implement different activities to ensure compliance with AstraZeneca standards of quality. These activities could include but are not limited to:

Contact the sites to:

- Provide information and support to the investigator(s)
- Confirm that the research team is complying with the protocol, and that data are being accurately recorded in the CRFs
- Ensure that the consent/assent documentation portion of the eligibility section of the Clinical CRF are signed, and screening scripts are stored at the investigator's site
- Ensure that the CRFs are completed properly and with adequate quality

Monitor activities for:

- Ensuring that consent/assent is documented in Patient Verbal Informed Consent Script and the Clinical CRF
- Evidera will host a 30-minute conference call with each clinical site for up to four (4) time points (touchpoints) at Months 1, 2, 3 (optional), and 6 to address site questions, and discuss a set of touchpoint questions that focus on the challenges and facilitators of implementing the PRECISION Tools.

Training of Study Site Personnel

The principal investigator will ensure that appropriate training relevant to the study is given to investigational staff and that any new information relevant to the performance of this study is forwarded to the staff involved.

6.1.3.2 ePRO Programming and Hosting

A Health Insurance Portability and Accountability Act (HIPAA)-compliant vendor specializing in electronic data capture will be responsible for the programming and hosting of the electronic patient-reported outcome (ePRO) data management system to collect and monitor data captured by the patient questionnaires. The quality assurance process will include extensive end-to-end testing, as well as a pre-test of data export and tabulations before launching with a live sample. During data collection, the web survey responses will be tracked by unique participant identifiers—not participant names.

Quantitative data from the clinical CRF will be transmitted via a secure SharePoint site directly into the electronic system database, DataFax. Data discrepancies will be identified and resolved.

6.1.3.3 DataFax CRF and Database Setup

The AIRQ™, the AIRQ™ 3-month Recall, Clinical CRF (which includes eligibility and consent documentation and the Asthma Checklist Assess content), the Follow-up Clinical CRF, and the Post-study Survey will be collected and managed using the DataFax system, according to Evidera's standard operating procedures (SOPs). Before data collection, data verification guidelines regarding out-of-range values, inconsistent responses, and data checks will be developed; and a testing of the DataFax system will be conducted.

CRF data will be optically entered into the study database upon transmittal via DataFax; once received, each CRF will be processed and reviewed by two trained project team members. The first-level reviewer will review all CRFs, while the second-level reviewer will review any items the first-level reviewer flagged or queried. Discrepancies or queries that are not resolved by the data entry staff will be forwarded to the sites for resolution.

6.1.3.4 Database Management

A database for all quantitative data collected in the interviews from the paper-completed questionnaires (e.g., AIRQ™, Clinical CRF) will be developed, tested, and validated using DataFax software. DataFax is a direct fax-to-computer (or PDF-to-computer) data management system that uses optical character recognition (OCR) software for collecting study CRFs that are sent directly into the system. DataFax is a Food and Drug Administration (FDA) Title 21 Code of Federal Regulations (CFR) Part 11 Compliant system that provides a time-stamped electronic audit trail for the creation, modification, or deletion of electronic data, and is required for studies seeking FDA regulatory submission.

